4 ELIGIBILITY CRITERIA

IBS Patients:

200 consecutive adult subjects \geq 18 years of age at screening who meet the following inclusion and exclusion criteria will be eligible for enrollment:

Inclusion criteria:

- Rome IV criteria for IBS-D
- Subjects will be asked to avoid Pepto-Bismol for 2 weeks prior to GHBT.
- Subjects will be instructed to avoid eating or drinking for 8 hours and avoid smoking for 6 hours prior to the test
- Have colonoscopy or sigmoidoscopy with mucosal biopsy within the past 2 years prior to enrollment
- Have an average score of 4 or higher over a 7-day pre-screen taking online symptom surveys assessing abdominal pain and bloating

Exclusion criteria:

- Underlying celiac disease
- Inflammatory bowel disease
- Other organic disease that could explain their symptoms.
- History of GI tract surgery, except for appendectomy
- Narcotics, antibiotics taken within 3 months or probiotics taken within one month prior to enrollment will not be permitted.
- Previously received formal dietary education, including a low FODMAP diet, for treatment of IBS.
- Previously received antibiotics, such as rifaximin, for treatment of IBS or SIBO.
- Women who are pregnant
- Women who are breastfeeding

Additional IBS subjects and Healthy Controls:

50 consecutive adult subjects \geq 18 years (25 IBS-D and 25 healthy controls) who are undergoing colonoscopy for clinical purposes (e.g. colon cancer screening)

For IBS subjects:

Inclusion criteria:

- Rome IV criteria for IBS-D

Exclusion criteria:

- Underlying celiac disease
- Inflammatory bowel disease
- Other organic disease that could explain their symptoms.
- History of GI tract surgery, except for appendectomy
- Narcotics, antibiotics taken within 3 months or probiotics taken within one month prior to enrollment will not be permitted.
- Women who are pregnant
- Women who are breastfeeding

For healthy controls:

Exclusion Criteria:

- History of chronic GI disorder, such as irritable bowel syndrome, inflammatory bowel disease, and small intestinal bacterial overgrowth
- Narcotics, antibiotics taken within 3 months or probiotics taken within one month prior to enrollment will not be permitted
- Women who are pregnant
- Women who are breastfeeding

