- 5) General risks (infrequent): This is an interventional study. IBS-D subjects' condition may worsen or improve while undergoing intervention with either rifaximin or a low FODMAP diet. Participation in this study will not prevent normal clinical care of IBS or its consequences. In addition, some prescribed medications may need to be stopped temporarily during the study. This includes medications that may influence pain sensation, including narcotic pain medications. IBS-D subjects will also be asked to discontinue antibiotics for at least 3 months and probiotics for at least 1 month prior to enrollment. IBS-D subjects will be asked to avoid Pepto-Bismol for at least 2 weeks prior to GHBT. IBS-D subjects will also be instructed to eat a low carbohydrate diet for at least 2 days prior to the GHBT to avoid inaccurate test results. If IBS-D subjects are taking any of these medications, their symptoms may return or worsen when they are stopped. However, the stopping of medications is temporary and is not felt to cause any undue hardship. Finally, there is a risk that some of the questions in the surveys may produce emotional distress. If the IBS-D subject desires, he/she can be referred to

a mental health specialist within the UMHS or another provider outside the UMHS system.

6) Risks for sharing samples (rare): If subjects decide to participate in an optional sub-study, saliva samples will be shared with Karolinska Institute and IKMB Kiel to evaluate differences in sucrase-isomaltase SNPs. There are potential risks to the IBS-D subject's privacy. However, all samples will be de-identified and only investigators at UMHS will have access to the linkage code.

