5 SUBJECT ENROLLMENT

Most patients with irritable bowel syndrome are seen in gastroenterology or general medicine clinics. IBS-D patients will be recruited from gastroenterology and general medicine clinics at Taubman Center and in the satellite clinics within the University of Michigan Health System. We will also be sending out letters to patients identified from DataDirect as eligible for the study. Eligible IBS-D subjects will be contacted and given material explaining the nature of the study and introduction to a low FODMAP diet. They will be given time to read the materials. If they choose to participate, they will undergo a one week pre-screening an 11-point numerical rating scale (NRS) for abdominal pain and bloating for 7 days. If the subjects qualify through the pre-screen, they will sign the consent document in the presence of the PI and/or Designee. IBS-D subjects will be enrolled on a first come, first served basis. This approach will ensure that IBS-D subjects are representative of the population of patients with IBS in Southeast Michigan.

Emails to providers in the General Medicine and Gastroenterology clinics in the University of Michigan System, public advertisements, telephone calls, and web postings on UMClinicalStudies.org will also be utilized to recruit IBS-D subjects.

IBS subjects who do not meet inclusion/exclusion criteria will not be enrolled in the study. All data collected from IBS-D subjects who are screen failures will be saved for data analysis.

IBS subjects and healthy controls who are undergoing colonoscopy will be approached in the Medical Procedures Unit to determine their interest in participating in the optional sub-study and to determine their eligibility.

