6 STUDY DESIGN AND PROCEDURES

Specific Aim 1: Randomize IBS-D subjects to receive either a nonabsorbable antibiotic rifaximin vs. low FODMAP dietary intervention.

1A. Research Approach:

200 IBS-D subjects will be carefully phenotyped using validated questionnaires (IBS symptoms, stool form, psychological function, quality of life) and diet analysis. IBS-D subjects will also undergo baseline testing including GHBT as well as fecal microbial analysis. IBS-D subjects will then be randomized to receive either rifaximin or low FODMAP diet intervention at the initial screening visit. Efficacy of therapies will be monitored with validated questionnaires to track symptomatic improvement. The primary outcome will be changes in mean daily pain or bloating after intervention compared with baseline. Responders to intervention will be defined as $\geq 30\%$ reduction in mean daily pain or bloating by visual analog scale (VAS) compared with baseline. Secondary outcomes will monitor changes in IBS-Symptom Severity Score as well as differences in GI symptoms, stool form, psychological function, quality of life, and dietary intake before and after intervention.

1B. Experimental Methods:

Subject Recruitment: 200 adult subjects ≥ 18 years of age who meet Rome IV criteria for IBS-D will be enrolled in the study. Women of childbearing age will undergo a urine pregnancy test to exclude the possibility of pregnancy. Women who are breastfeeding will also be excluded. IBS-D subjects will be excluded if they have underlying celiac disease, inflammatory bowel disease, or other organic disease that could explain their symptoms. All IBS-D subjects will have prior sigmoidoscopy or colonoscopy with mucosal biopsies within the past 2 years to rule out microscopic colitis. IBS-D subjects with a history of GI tract surgery, except for appendectomy, will also be excluded from the study. Antibiotics taken within 3 months prior to enrollment will not be permitted (54). IBS-D subjects on probiotics must discontinue their use at least 1 month prior to fecal collection. IBS medications, including anti-depressants, will be allowed if the dose has been stable for at least 1 month before inclusion. Medications will be carefully tracked to follow any potential confounding issues. IBS-D subjects who have previously received formal

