We will develop and validate a predictive model of response to low FODMAP diet using data from the subjects randomized to a low FODMAP diet (Aim 1) combined with existing data from a separate cohort of IBS-D subjects previously treated with a low FODMAP diet (HUM 00053274).

3B. Experimental Methods:

We will use the combined cohort of patients treated with a low FODMAP diet (Aim 1 and HUM #00053274), which will be split into a training set from a random sample of 80% of the data while the remaining 20% of the data will serve as the test set. Using a random forest model, 5x2 nested cross-validation (CV) will be performed within the training set for model selection and hyperparameter tuning. The candidate models will be compared by testing for overlap of confidence intervals for area under the curves (AUCs, two-sided test). Once a final model is selected, model performance will be evaluated on the test set.

Study Timeline:

Figure 1 IBS Subject Timeline

Schedule of Events - Low FODMAP Group

Visit Number	Pre-Visit	Visit 1	Visit 2	Visit 3	Visit 4	Visit 5
Visit Description	Pre-screening (Phone/in person)	Baseline (Phone/in person)	Monitoring (Phone/in person)	Monitoring (Phone/in person)	Monitoring (Phone/in person)	Monitoring/Outcomes (Phone/in person)
Time point	Eligibility	Day 0	Day 7±3 days	Day 14±3 days	Day 28±3 days	Day 35±3 days
7 day pre-screening questionnaire	X					
Informed Consent	X					
Medical History /Physical Examination		X	X	X	X	X
Urine pregnancy test (Females of childbearing age)		X				
Washout	X					
Questionnaires		X		X		X

3-day food diary		X				
24-hour dietary recall			X	X	X	X
GI nutrition consultation		X		X		
Colonoscopy with mucosal biopsies (optional)	X					
Serum Cytokine Profiles (optional)		X				X
Buccal swab collection (optional)		X				
Glucose hydrogen breath testing		X				X
Stool collection for fecal microbial analysis		X (3 baseline samples)		X	X	X
Randomization	X					
Dietary Compliance			X	X	X	X
Adverse Events Monitoring			X	X	X	X

*Female participants capable of bearing children will be required to attend visit 1 in person for the pregnancy test

*During COVID-19 pandemic, all hydrogen breath tests will be conducted remotely

Schedule of Events – Rifaximin Group

*Female participants capable of bearing children will be required to attend visit 1 in person for the pregnancy test

*During COVID-19 pandemic, all hydrogen breath tests will be conducted remotely

Visit Number	Pre-Visit	Visit 1	Visit 2	Visit 3	Visit 4	Visit 5

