10 STATISTICAL CONSIDERATIONS

Aim 1:

All of the interventional analyses will be analyzed on an intention-to-treat basis. Each IBS-D subject will act as his/her own control for analysis of the effects of either rifaximin or low FODMAP diet intervention. This paired design inherently eliminates a significant amount of bias/confounding and affords increased statistical power. We will power our study to detect a $\geq 30\%$ improvement in mean daily bloating or abdominal pain after intervention compared with baseline. Using available data from a US study on low FODMAP diet in IBS patients (42), we conservatively estimate that we will require 14 IBS-D subjects in each arm to have $>90\%$ power to detect a mean difference of 1.7 in abdominal bloating scores after intervention via paired t-tests with the expected standard deviation (SD) of ± 1.8 . Thus, our expected enrollment of 32 IBS-D subjects in each arm will be more than sufficient for analyzing this aim (see biostatistical analysis for Aim 2), even if the SD is nearly two-fold larger than expected.

Aim 2:

We will examine both inter- and intra-individual variability in microbiota-derived metrics. We plan to use a paired design to eliminate a significant amount of bias/confounding and increase statistical power. We anticipate that there will be some variability in the three samples collected prior to treatment, and various techniques will be employed to average these data so they are incorporated as the baseline. For example, for α diversity (Shannon index) a simple average of the three time points will be sufficient to

establish a baseline α diversity. Similar techniques will be applied to other community structure metrics, to create “deltas” between post-treatment time points and the baseline.

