11.3 Data Safety Monitoring Plan

11.3.1. Oversight Responsibilities

Oversight of the trial is provided by the Principal Investigator (PI), [name]. [name] assures that informed consent is obtained prior to performing any research procedures, that all subjects meet eligibility criteria, and that the study is conducted according to the IRB-approved research plan.

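### The baseline window for the primary outcome is undefined, and the only multi-day symptom record scheduled before Day 0 is the week that selects patients on a high score

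*Combined protocol and SAP*

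**What the plan says.** Section 4 (Eligibility Criteria) admits patients who "Have an average score of 4 or higher over a 7-day pre-screen taking online symptom surveys assessing abdominal pain and bloating". Section 5 (Subject Enrollment) describes this as a "one week pre-screening an 11-point numerical rating scale (NRS) for abdominal pain and bloating for 7 days", and adds: "If the subjects qualify through the pre-screen, they will sign the consent document in the presence of the PI and/or Designee".

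Sections 2 and 6 define the primary outcome as change from baseline in mean daily pain or bloating, and a responder as a patient with a reduction of at least 30%. Neither section gives the baseline days. In both Schedule of Events tables the "7 day pre-screening questionnaire" is the only multi-day symptom row before Day 0. The 3-day diary at Visit 1 records food. Section 6 also lists an NRS completed at baseline, with no number of days, and a daily diary card, with no start day.

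Section 10, Aim 1, plans a paired t-test: "Each IBS-D subject will act as his/her own control for analysis of the effects of either rifaximin or low FODMAP diet intervention". It describes no between-arm test of the primary outcome.

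**The concern.** A week used to admit only patients averaging 4 or more is, on average, a bad week for those admitted. Part of its height is temporary and will be gone at the next measurement, whatever the treatment does. If the same week is the baseline, this fall enters the primary change in full. Section 10 says that pairing removes much bias, but pairing does not remove this one. Both arms would look more effective than they are, and some patients would be labelled responders without having responded. That label is then related to SIBO and microbiota in Aim 2, and is the outcome of the prediction model in Aim 3.

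The other readings are no safer. A single-day NRS at baseline is not a mean daily score, and diary days after Day 0 are already on treatment. Leaving the window open also allows it to be chosen after the data are seen.

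**Working it through.** **1. The plan's own figure.** Inputs from Section 10: difference 1.7, SD 1.8 (read as the SD of the paired difference), paired t-test. Alpha is not stated; 0.05 two-sided is assumed. The noncentral t distribution gives 90.4% power at 14 patients and 87.8% at 13, so the stated 14 per arm reproduces. The calculation makes no allowance for a fall caused by selection.

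**2. Expected fall with no treatment effect.** Let μ and s be the mean and SD of the 7-day score among those screened, and ρ the correlation between two such weeks. The documents give none of these, so all are assumed. If the selecting week is the baseline:

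fall = (1 − ρ) × s × φ(a) / (1 − Φ(a)), with a = (4 − μ)/s.

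With s = 2 and ρ = 0.7:
- μ = 4: 0.3 × 2 × 0.3989/0.5000 = 0.48
- μ = 5: 0.3 × 2 × 0.3521/0.6915 = 0.31
- μ = 6: 0.3 × 2 × 0.2420/0.8413 = 0.17

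**3. False ≥30% responders.** These come from simulating a true score plus independent weekly error, truncated to 0–10, with entry if the pre-screen week is at least 4 and no treatment effect. A later week is compared with the selecting week, or with a fresh second week. One score is modelled, because the plan does not say how pain and bloating combine in the entry rule.

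| μ, s, ρ | Spurious fall | Share of 1.7 | False responders: selecting v fresh week |
|---|---|---|---|
| 4, 2.0, 0.5 | 0.80 | 47% | 31% v 21% |
| 4, 2.0, 0.7 | 0.48 | 28% | 20% v 13% |
| 5, 2.0, 0.7 | 0.31 | 18% | 15% v 11% |
| 5, 1.5, 0.8 | 0.13 | 8% | 4% v 3% |
| 6, 2.0, 0.7 | 0.17 | 10% | 10% v 8% |
| 6, 1.5, 0.8 | 0.05 | 3% | 2% v 2% |

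The first and last rows are the extremes of the grid. With the fresh week the mean spurious change is about 0 throughout, because the simulated errors are independent.

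**4. Tied to the plan's SD of 1.8.** Setting s√(2(1 − ρ)) = 1.8 gives ρ = 1 − 1.8²/(2s²), which is 0.50, 0.60 and 0.74 for s = 1.8, 2.0 and 2.5. The fall is then 0.52–0.72 at μ = 4, 0.36–0.43 at μ = 5 and 0.22–0.24 at μ = 6. Treating it as the noncentrality, the nominal 5% paired test would be significant with no treatment effect in 10% to 59% of trials at 32 per arm (Section 10). At 100 per arm (the 200 of Sections 4 and 6, split 1:1) the range is 23% to 98%.

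**5. Order of pre-screen, consent and washout.** Consent follows the pre-screen in Section 5, yet Section 11.3.1 says that the PI "assures that informed consent is obtained prior to performing any research procedures". Section 6 says "IBS-D subjects on probiotics must discontinue their use at least 1 month prior to fecal collection", while Sections 3 and 4 count the probiotic-free month back from enrollment. Section 3 also expects some medicines to be stopped during the study and warns: "If IBS-D subjects are taking any of these medications, their symptoms may return or worsen when they are stopped". Both schedules put pre-screen, consent and washout in one Pre-Visit column without an order.

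**The case against.** The strongest reply is that nothing in the protocol makes the pre-screen the baseline. Sections 4 and 5 use it for eligibility only, and Section 6 has a baseline NRS and a diary whose start is open. This stands. A reader might infer that the primary estimate is biased as planned; the documents support only the conditional statement.

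A reader might also infer that the pre-screen comes before washout, leaving symptom scores that are out of date and taken on a product later withdrawn. That is possible but not shown. If enrollment means consent, and consent promptly follows the pre-screen, a compliant probiotic user had stopped weeks earlier.

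On size, the inputs are assumed. A screening mean of 4 implies that about half of those screened fail, and at mean 6 the fall is at most 0.29 on this grid. The 31% is not the effect of selection either, since a fresh week would still give 21%. Nor is the net direction fixed: worsening after a medicine is stopped would act against the spurious fall. The harm to Aims 2 and 3 has not been quantified.

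Finally, selection drift cancels in expectation between randomised arms, so a between-arm test would deal with it. That is right for the treatment contrast. But no such test is planned, and it would not correct the responder label within an arm, which is what Aim 3 uses.

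**Conclusion.** The point holds as a gap in definition with a conditional bias. The baseline window is not stated, the only scheduled multi-day candidate is the week that selects on a high score, and the uncontrolled paired analysis cannot separate regression to the mean from benefit. If that week is used, the spurious fall is about 0.05 to 0.8 points (3% to 47% of 1.7), and false responders exceed those from a fresh week by about 0 to 10 percentage points. These ranges rest on an assumed screening mean of 4 to 6, SD 1.5 to 2.0, correlation 0.5 to 0.8, a single score and independent weekly errors. More patients per arm would not reduce the bias, only make a false significant result more likely. The washout order is a matter for reconciliation, not a demonstrated fault.

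**What to change.** - Use the pre-screen for eligibility only. Define baseline, for both the primary change and the responder rule, as the mean daily NRS over a separate 7-day window after the pre-screen and any washout and before treatment starts. Add the row to both schedules, and do not re-apply the ≥4 rule to that week. Both schedules mark randomization at the Pre-Visit, so the week is best completed before allocation is disclosed.
- Settle how the window deals with the low-carbohydrate days that Section 3 requires before the breath test at Visit 1, since they fall near it and may affect bloating.
- Reconcile the order of pre-screen, consent and washout across Sections 3, 4, 5, 6 and 11.3.1 and the schedules.
- Consider a between-arm comparison of change for the primary outcome. With SD 1.8 and 90% power, the detectable difference is 1.8 × 3.24 × √(2/n): about 1.46 points at 32 per arm and 0.83 at 100.

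The new week removes all the selection drift only if errors in the two weeks are independent. If the pre-screen correlates 0.60 with follow-up and 0.65 with the new week, (0.65 − 0.60)/(1 − 0.60), about 13%, remains; at 0.85 about 63% would.

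The cost is a protocol amendment, one more week of the existing online survey, up to a week's delay to Day 0, and a slightly less favourable observed change. No extra visit is needed.

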5 SUBJECT ENROLLMENT

Most patients with irritable bowel syndrome are seen in gastroenterology or general medicine clinics. IBS-D patients will be recruited from gastroenterology and general medicine clinics at Taubman Center and in the satellite clinics within the University of Michigan Health System. We will also be sending out letters to patients identified from DataDirect as eligible for the study. Eligible IBS-D subjects will be contacted and given material explaining the nature of the study and introduction to a low FODMAP diet. They will be given time to read the materials. If they choose to participate, they will undergo a one week pre-screening an 11-point numerical rating scale (NRS) for abdominal pain and bloating for 7 days. If the subjects qualify through the pre-screen, they will sign the consent document in the presence of the PI and/or Designee. IBS-D subjects will be enrolled on a first come, first served basis. This approach will ensure that IBS-D subjects are representative of the population of patients with IBS in Southeast Michigan.

Emails to providers in the General Medicine and Gastroenterology clinics in the University of Michigan System, public advertisements, telephone calls, and web postings on UMClinicalStudies.org will also be utilized to recruit IBS-D subjects.

IBS subjects who do not meet inclusion/exclusion criteria will not be enrolled in the study. All data collected from IBS-D subjects who are screen failures will be saved for data analysis.

IBS subjects and healthy controls who are undergoing colonoscopy will be approached in the Medical Procedures Unit to determine their interest in participating in the optional sub-study and to determine their eligibility.

6 STUDY DESIGN AND PROCEDURES

Specific Aim 1: Randomize IBS-D subjects to receive either a nonabsorbable antibiotic rifaximin vs. low FODMAP dietary intervention.

1A. Research Approach:

200 IBS-D subjects will be carefully phenotyped using validated questionnaires (IBS symptoms, stool form, psychological function, quality of life) and diet analysis. IBS-D subjects will also undergo baseline testing including GHBT as well as fecal microbial analysis. IBS-D subjects will then be randomized to receive either rifaximin or low FODMAP diet intervention at the initial screening visit. Efficacy of therapies will be monitored with validated questionnaires to track symptomatic improvement. The primary outcome will be changes in mean daily pain or bloating after intervention compared with baseline. Responders to intervention will be defined as $\geq 30\%$ reduction in mean daily pain or bloating by visual analog scale (VAS) compared with baseline. Secondary outcomes will monitor changes in IBS-Symptom Severity Score as well as differences in GI symptoms, stool form, psychological function, quality of life, and dietary intake before and after intervention.

1B. Experimental Methods:

Subject Recruitment: 200 adult subjects ≥ 18 years of age who meet Rome IV criteria for IBS-D will be enrolled in the study. Women of childbearing age will undergo a urine pregnancy test to exclude the possibility of pregnancy. Women who are breastfeeding will also be excluded. IBS-D subjects will be excluded if they have underlying celiac disease, inflammatory bowel disease, or other organic disease that could explain their symptoms. All IBS-D subjects will have prior sigmoidoscopy or colonoscopy with mucosal biopsies within the past 2 years to rule out microscopic colitis. IBS-D subjects with a history of GI tract surgery, except for appendectomy, will also be excluded from the study. Antibiotics taken within 3 months prior to enrollment will not be permitted (54). IBS-D subjects on probiotics must discontinue their use at least 1 month prior to fecal collection. IBS medications, including anti-depressants, will be allowed if the dose has been stable for at least 1 month before inclusion. Medications will be carefully tracked to follow any potential confounding issues. IBS-D subjects who have previously received formal

dietary education for IBS, including a low FODMAP diet, or previously received antibiotics, including rifaximin, for treatment of IBS-D or SIBO will be excluded from the study.

GI Symptom Assessment: All IBS-D subjects will complete validated questionnaires to quantify severity of IBS symptoms, including IBS Symptom Severity Scale (IBS-SSS), Gastrointestinal Symptom Rating Scale-IBS (GSRS-IBS), an 11-point numerical rating scale (NRS) for abdominal pain and bloating, and Bristol Stool Form Scale (BSFS) at baseline (55–58). The NRS for abdominal pain and bloating and the BSFS will be completed online through the REDCap Survey Tool.

Psychological and Quality of Life Assessment: IBS-D subjects will also complete validated questionnaires to assess for presence of and to measure severity of psychological disorders, GI specific anxiety, and impairments in quality of life. All IBS-D subjects will complete the Patient Health Questionnaire (PHQ-9), Visceral Sensitivity Index (VSI), and IBS-quality of life (IBS-QOL) (59–61). The PHQ-9 will be reviewed by the study team within 24 hours of completing the questionnaire. If a subject answers affirmative to the question “Thoughts that you would be better off dead or of hurting yourself in some way,” they will be provided with the appropriate referral to mental health counseling and/or the subject’s PCP will be alerted.

Dietary Assessment: All IBS-D subjects will undergo initial consultation with the study team and will be instructed on how to monitor and record their dietary intake. IBS-D subjects will then record daily their dietary intake for 3 days prior to fecal collection.

Fecal Collection and Preparation: Three fresh stool samples will be collected from all IBS-D subjects at baseline. Each sample will be immediately placed into an OMNIgene•GUT collection tube (DNA Genotek, Inc., Ottawa, ON, Canada) which allows for self-collection and stabilization of fecal DNA samples for up to 60 days at ambient temperature (62). Samples will then be mailed back or picked up by the study team and stored at -80°C in [name]’s Lab for long-term storage. If patients consent to the optional portion of the study, they will provide a stool sample in 95% ethanol at Visits 1, 3, 4, and 5. We will also collect a one-time stool sample and symptom questionnaires from healthy controls. Healthy controls will not have a history of gastrointestinal conditions and do not report any abnormal bowel movements or abdominal pain.

Tryptophan hydroxylase-1 (TpH-1) and sucrase-isomaltase single nucleotide polymorphisms (SNPs): Buccal swabs will be collected from all IBS-D subjects at baseline. Each sample will be immediately placed into an Oragene•DISCOVER (DNA Genotek, Inc., Ottawa, ON, Canada) which allows for stabilization of salivary DNA samples for up to 5 years at ambient temperature. Samples will then be stored at -80°C for long-term storage. De-identified DNA samples will be shared with Karolinska Institute and IKMB Kiel to analyze differences in sucrase-isomaltase SNPs. This portion of the study is optional and subjects have a choice to allow their saliva samples to be stored for this sub-study.

Serum cytokine profiles: Serum cytokines, including TNF- α , IL-1 β , IL-6, IL-8, and IL-10 will be measured at baseline and at week 5. Whole blood will be collected in a 10 ml SST tube. SST tubes will be allowed to clot at room temperature for 30 minutes. The serum will then be separated from the red blood cells by spinning for 15 min at 1300G at 4°C. The serum will then be aliquoted from each blood collection tube into (3) 2-ml transfer tubes and stored at -80°C for

future analyses. This portion of the study is optional and subjects have a choice to allow their blood samples to be stored for this sub-study

Glucose Hydrogen Breath Test (GHBT): SIBO will be diagnosed using the glucose H₂/CH₄ breath test as previously described (63). Briefly, H₂/CH₄ breath concentrations will be measured by gas chromatography (Quintron Instrument Company, Milwaukee, USA) in parts per million (ppm) after administration of an oral loading dose of glucose (75 g in 250 ml of sterile water). Breath samples will be collected every 15 minutes for a total of 120 minutes. The test will be considered positive for SIBO when H₂ and/or CH₄ increase by ≥ 12 ppm above baseline. COVID-19 modifications: Patients will be given take home hydrogen test kits either in person or through the mail to conduct the test at home. Instructions will be given prior to test with the take home test kit. Patients could bring the test result back either in person or through mail and the lab will analyze the results.

Trial Protocol: In order to minimize unequal allocation between arms, IBS-D subjects will be randomized using block randomization with random permuted sizes of 2 or 4 in a 1:1 ratio into two arms: one group will undergo treatment with rifaximin 550 mg three times daily for 14 days. The second group will be placed on a low FODMAP diet (≤ 9 grams per day as previously described) for 4 weeks (40,64,65). IBS-D subjects undergoing dietary intervention will undergo consultation with a bionutritionist knowledgeable in low FODMAP diets. A diet plan will be implemented and individualized to subjects based on information from their dietary history. Written information regarding allowable vs. non-allowable food items will be provided to IBS-D subjects and bionutritionists will be available during the study for further education. IBS-D subjects randomized to the low FODMAP diet group will meet with the GI nutritionist at the completion of the 2nd week of dietary intervention to answer any potential questions regarding the diet. IBS-D subjects will complete a 24-hour dietary recall each week or every two weeks during the 4-week dietary intervention to ensure compliance.

Symptom Assessment: IBS-D subjects will record stool frequency, BSFS, and symptom scores for abdominal pain and bloating daily on a diary card. IBS-D subjects will complete questionnaires on a weekly basis during study visits to determine changes in symptoms. Responders to intervention arm (both rifaximin and low FODMAP diet) will be defined as $\geq 30\%$ reductions in mean daily pain or bloating compared with baseline. Secondary outcomes, including reduction in IBS Symptom Severity Scale by ≥ 50 compared with baseline at the end of the interventional arm, will also be monitored. These are both considered to reflect clinically meaningful improvements in IBS (55,57). IBS-D subjects will be seen on a weekly or biweekly basis and diary cards will be collected. Adherence to medications or dietary intervention will also be assessed at that time.

Specific Aim 2: Determine using longitudinal analyses how SIBO status and fecal microbiota-derived metrics associate with response to treatment with rifaximin or a low FODMAP dietary intervention.

2A. Research Approach:

We will prospectively follow the results of GHBT and fecal microbiota before and after treatment with rifaximin and low FODMAP dietary restriction. We will collect fecal samples throughout the study period in IBS-D patients. All IBS-D subjects will also undergo GHBT before and after

intervention. The primary aim will be change in fecal microbial diversity after intervention with rifaximin or low FODMAP diet compared with baseline. Secondary outcomes will evaluate whether response to treatment with rifaximin or low FODMAP diet is associated with: (i) presence of SIBO on initial testing, (ii) persistence of SIBO after intervention, (iii) changes in α - and β - diversity as well as in dominant phyla. We will also utilize human intestinal enteroids to model how host-microbial interactions may influence response to treatment with rifaximin or low FODMAP diet in IBS.

2B. Experimental Methods:

Fecal Collection and Preparation: Stool samples will be collected from all IBS-D subjects at weeks 2, 4 and 5 as described in Aim 1. Stool samples will be stored for up to 5 years at the conclusion of the study for future analyses, including evaluating differences in metabolomics, such as histamine, p-hydroxybenzoic acid, azelaic acid, and H₂ (45). This portion of the study is optional, and subjects have a choice to allow their stool samples to be stored for this sub-study. This may provide mechanistic descriptions of how changes in gut microbiota lead to changes seen in IBS. If patients consent to this optional portion of the study, they will provide a stool sample in 95% ethanol at weeks 0, 2, 4, and 5. Subjects will be compensated a nominal amount of \$20 for stool samples returned at week 0 and \$10 each for weeks 2, 4 and 5 to express our gratitude for their participation in the study. We will also provide mailers to mail back samples to minimize study burden on participants.

GHBT: Glucose H₂/CH₄ test will be repeated at week 5 as described in Aim 1.

Serum cytokine profiles: Serum cytokines will be repeated at week 5 as described in Aim 1. Handling and processing of the blood will be described in Appendix 1.

Mucosal Samples: If subjects consent to participate in this optional sub-study, mucosal biopsies will be taken from eligible subjects who are scheduled to undergo a colonoscopy for clinical purposes (e.g. to rule out alternative causes of symptoms or screening for colon cancer). In addition to the IBS subjects recruited to participate in the clinical trial, we will recruit an additional 25 IBS subjects as well as 25 healthy controls undergoing colonoscopy for clinical purposes (e.g. colon cancer screening) to determine how host-microbial interactions may impact on IBS vs. healthy controls.

Mucosal biopsies will be utilized to generate human intestinal enteroids to study host-microbial interactions determining response to treatment in IBS. Four mucosal biopsies will be obtained from normal appearing mucosa in the ileum, ascending and sigmoid colon (total of 12 mucosal biopsies per patient), placed in a sterile cryovial on ice, and immediately stored at -80°C for long-term storage.

Sequencing and Data Analysis:

(i) MiSeq Illumina Sequencing: DNA samples will be submitted to the University of Michigan Host Microbiome Initiative under the Microbiome Explorers Program and will be processed using the MiSeq Illumina sequencing platform. 16S rRNA gene libraries will be constructed using primers specific to the V4 region.

(ii) OTUs and Diversity Measurements: The open-source software program, Mothur, will be used following the steps outlined in the Mothur MiSeq SOP (66,67). The 16S rRNA gene sequencing profiles will be assessed using metrics for α diversity (such as Shannon or inverse-

Simpson indices) and β diversity-based distance measures between samples, such as θ_{yc} or Bray-Curtis (68,69). Community types will be identified using unsupervised clustering algorithms, and individual operational taxonomic units (OTUs) will be identified and compared between/within patients (see Biostatistical analysis).

(iii) Quantitative PCR Targeting the 16S rRNA Gene: qPCR will be used to quantify the total number of 16S rRNA gene copies/gram. Reactions will be performed on a CFX Connect Real-Time PCR detection system (Bio-Rad Laboratories; Hercules, CA) with universal 16S rRNA gene primers as previously described (33).

Specific Aim 3: Develop a predictive model to identify subsets of IBS-D patients responsive to treatment.

3A. Approach:

We will develop and validate a predictive model of response to low FODMAP diet using data from the subjects randomized to a low FODMAP diet (Aim 1) combined with existing data from a separate cohort of IBS-D subjects previously treated with a low FODMAP diet (HUM 00053274).

3B. Experimental Methods:

We will use the combined cohort of patients treated with a low FODMAP diet (Aim 1 and HUM #00053274), which will be split into a training set from a random sample of 80% of the data while the remaining 20% of the data will serve as the test set. Using a random forest model, 5x2 nested cross-validation (CV) will be performed within the training set for model selection and hyperparameter tuning. The candidate models will be compared by testing for overlap of confidence intervals for area under the curves (AUCs, two-sided test). Once a final model is selected, model performance will be evaluated on the test set.

Study Timeline:

Figure 1 IBS Subject Timeline

Schedule of Events - Low FODMAP Group

Visit Number	Pre-Visit	Visit 1	Visit 2	Visit 3	Visit 4	Visit 5
Visit Description	Pre-screening (Phone/in person)	Baseline (Phone/in person)	Monitoring (Phone/in person)	Monitoring (Phone/in person)	Monitoring (Phone/in person)	Monitoring/Outcomes (Phone/in person)
Time point	Eligibility	Day 0	Day 7±3 days	Day 14±3 days	Day 28±3 days	Day 35±3 days
7 day pre-screening questionnaire	X					
Informed Consent	X					
Medical History /Physical Examination		X	X	X	X	X
Urine pregnancy test (Females of childbearing age)		X				
Washout	X					
Questionnaires		X		X		X

3-day food diary		X				
24-hour dietary recall			X	X	X	X
GI nutrition consultation		X		X		
Colonoscopy with mucosal biopsies (optional)	X					
Serum Cytokine Profiles (optional)		X				X
Buccal swab collection (optional)		X				
Glucose hydrogen breath testing		X				X
Stool collection for fecal microbial analysis		X (3 baseline samples)		X	X	X
Randomization	X					
Dietary Compliance			X	X	X	X
Adverse Events Monitoring			X	X	X	X

*Female participants capable of bearing children will be required to attend visit 1 in person for the pregnancy test

*During COVID-19 pandemic, all hydrogen breath tests will be conducted remotely

Schedule of Events – Rifaximin Group

*Female participants capable of bearing children will be required to attend visit 1 in person for the pregnancy test

*During COVID-19 pandemic, all hydrogen breath tests will be conducted remotely

Visit Number	Pre-Visit	Visit 1	Visit 2	Visit 3	Visit 4	Visit 5
